8.3.2 Secondary Endpoint(s)

8.3.2.1 Overall Survival

Overall survival is the time between the date of randomization and the date of death. For subjects without documentation of death, OS will be censored to the last date the subject was known to be alive.

8.3.2.2 Overall Survival Rate

The overall survival rate at 1, 2, and 3 years is defined as the probability that a subject is alive at 1, 2, and 3 years, respectively, following randomization.

8.3.3 Exploratory Endpoint(s)

- Safety and tolerability objective will be measured by the incidence of adverse events (AEs), serious adverse events (SAEs), deaths, and laboratory abnormalities.
- DMFS is defined as the time between the date of randomization and the date of first distant recurrence or date of death (whatever the cause), whichever occurs first. For subjects who remain alive and distant recurrence-free, DMFS will be censored on the date of last disease assessment.
- The objective to evaluate PD-L1 status as a predictive biomarker will be measured by the primary endpoint of DFS and the secondary endpoint of OS based on PD-L1 status level.
- The objective to evaluate PD-L1 status prior to CRT and at the time of surgery will be measured by the mean change in PD-L1 status level and by the proportion of PD-L1 positive and negative subjects.
- Pharmacokinetics will be measured using serum concentration-time data.
- PFS2 is defined as the time from randomization to the date of investigator-defined documented objective disease progression on the subsequent next-line therapy or start of second subsequent next-line therapy or death due to any cause, whichever comes first. Details for censoring will be provided in the SAP.

Assessments for other exploratory endpoints including biomarker analysis, immunogenicity, and outcomes research are discussed in [Sections 5.6](#) and [5.8](#), respectively. Corresponding endpoints will be detailed in the SAP(s).

8.4 Analyses

8.4.1 Demographics and Baseline Characteristics

Demographic and baseline characteristics will be summarized by treatment arm as randomized using descriptive statistics for all randomized subjects.

8.4.2 Efficacy Analyses

8.4.2.1 Protection of Type-I Error

For the analysis purposes of primary endpoint of DFS and the first secondary endpoint of OS, the overall hierarchical approach⁶⁴ will be used

The details will be provided in the statistical analysis plan (SAP).

8.4.2.2 Primary Efficacy Endpoint

DFS will be compared between treatment arms

8.4.2.3 Secondary Efficacy Endpoints

Overall survival will be

Survival rate analysis will be carried out only for those time points which are mature enough by the time of the given database-lock.

No formal statistical comparison between the 2 arms will be performed on the survival rate.

8.4.2.4 Exploratory Efficacy Endpoints

The HR for DMFS and PFS2 will be estimated via a Cox model with treatment arm as the only covariate in the model.

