APPENDIX 5 PROTOCOL AMENDMENT SUMMARY OF CHANGE HISTORY

OVERALL RATIONALE FOR REVISED PROTOCOL 03

The rationale for study design changes include factors observed during the conduct of the trial. The actual enrollment in the study has been much slower than initial projections. The enrollment period was re-estimated to be 26 months (versus 15 months in the original protocol) in the Revised Protocol 02 (04-May-2017). More recently it was re-projected to approximately [REDACTED]

When evaluating the impact of the slow enrollment to the study design and conduct, published external data related to the study population were examined and the impact on study assumptions in the control arm were evaluated. The data from the chemoradiotherapy followed by surgery (CRT + S) arm in the CROSS trial with long-term follow up (CROSS LT) was considered the most relevant data to the study population. In consultation with external clinical experts and using data from the CROSS LT trial, it was concluded that the median disease-free survival (DFS) and overall survival (OS) in the placebo arm should be much longer than the original assumption. [REDACTED]

[REDACTED] Therefore, changes in the study design were needed in order to ensure that the study is adequately powered.

Given the above considerations and the rationale in [Section 1.4.7.1](#) of Revised Protocol 03, the following major changes were made:

- 1) DFS has become the single primary endpoint in the study and OS changed from a co-primary endpoint to the first secondary endpoint to be tested hierarchically.
- 2) Progression-free survival after the next line of subsequent therapy (PFS2) has been added as an exploratory endpoint to the study per recent EMA guidance. PFS2 has recently been proposed as a surrogate for OS, particularly for trials evaluating maintenance therapy.

[REDACTED] were held prior to this protocol revision. Revisions apply to future subjects enrolled in the study, and where applicable, to all subjects currently enrolled.

SUMMARY OF KEY CHANGES FOR REVISED PROTOCOL 03		
Section Number & Title	Description of Change	Brief Rationale
Synopsis 1.3.1, Primary Objectives; 1.3.2, Secondary Objectives	Moved overall survival (OS) from co-primary objective to secondary objective.	See overall rational for the revised protocol above.

SUMMARY OF KEY CHANGES FOR REVISED PROTOCOL 03		
Section Number & Title	Description of Change	Brief Rationale

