5.2 Assumptions of the Treatment Effect

Assumption for DFS

An average HR of 0.72 is assumed for DFS between nivolumab and placebo in CA209577 at the final DFS analysis, which accounts for the piece-wise HRs summarized in Table 5.1-1. This translates to a median DFS of 31 months in the nivolumab arm.

In many trials studying immunotherapies, the PFS and OS curves in the immunotherapy-treated arms tend to have a delayed separation from the control arms across tumor indications;¹⁰ therefore, the treatment effect for DFS is assumed to have a delayed separation with an HR of 1 for the first 3 months and a larger treatment effect after delayed separation with an HR of 0.667. After 5 years, the treatment effect for DFS is assumed to decrease slightly with an HR of 0.8. This takes into consideration that patients who have not had disease recurrence within 5 years of surgery are generally cured from the disease and the treatment effect is more reflective of the survival benefit.

Assumption for OS

The average HR of 0.73 is assumed for OS between nivolumab and placebo in CA209577 at the final OS analysis, which accounts for the piece-wise HRs summarized in Table 5.1-2. This translates to median OS of 44 months in the nivolumab arm.

The assumption of the OS treatment effect between the 2 arms follows the same thought process as the assumption of the DFS treatment effect. The treatment effect for OS is assumed to have a delayed separation with HR of 1 for the first 4 months, and a larger treatment effect after delayed separation with an HR of 0.685. After 6 years, the treatment effect for OS is assumed to decrease slightly with an HR of 0.8. This takes into consideration the combined effect of potential for more subsequent immunotherapies in the control arm and other effective subsequent therapies in both arms for long-term survivors.

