7.5.2 Primary Efficacy Endpoint

DFS will be compared between treatment arms using a two-sided log rank test, stratified by the three randomization stratification factors as recorded in IWRS.

The HR for DFS with its corresponding two-sided $100 \times (1 - \text{adjusted } \alpha)\%$ CI will be estimated via a stratified Cox model with treatment arm as the only covariate in the model. Adjustment on the CI will be based on the reallocated alpha level.

DFS for each treatment arm will be estimated and plotted using the KM product-limit method. Median survival time will be computed using the KM estimate and a 95% CI for the median will be computed based on a log-log transformation of the survivor function.

Source of DFS Event

The source of DFS event will be summarized by treatment group:

- Recurrence (local recurrence, regional recurrence, distant recurrence)
- Death

Status of Censored Subjects

The status of subjects who are censored in the DFS KM analysis will be tabulated for each randomized treatment group using the following categories:

- 1) Censored on randomization date
 - a) no baseline disease assessment
 - b) no on-study disease assessment and no death
 - c) no on-study disease assessment but death with prior subsequent therapy or second primary cancer
- 2) Censored on date of last evaluable disease assessment on-study
 - a) Received subsequent anti-cancer therapy
 - b) Second non-esophageal and non-GEJ primary cancer
 - c) Still on treatment
 - d) In follow-up
 - e) Off study
 - i) lost to follow-up
 - ii) subject withdrew consent
 - iii) other

DFS rates at fixed time points (e.g. 6 months, depending on the minimum follow-up) will be presented along with their associated 95% CIs. These estimates will be derived from the Kaplan-Meier estimate and corresponding CIs will be derived based on Greenwood formula for variance derivation and on log-log transformation applied on the survivor function.

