7.5.2.1 Sensitivity Analyses

The following four sensitivity analyses are planned for DFS to evaluate the robustness of the primary analysis of DFS.

- *Stratified analysis using stratification factors as obtained from the baseline CRF pages (instead of IWRS).* This analysis will be performed only if the stratification factors at randomization (as per IWRS) and baseline are not concordant for at least 10% of all randomized subjects considering all three stratification factors together.
- *Analysis using a 2-sided, un-stratified log-rank test and an un-stratified Cox proportional hazards model with treatment as the single covariate*
- *Analysis for subjects with no relevant deviation and those receiving at least one dose of study drug (per protocol subjects).* This analysis will be conducted only if there are more than 10% subjects with relevant protocol deviations.

Each of the above analysis will use the same significance level as the corresponding primary analysis. Estimate of the HR, its two sided $100(1-\alpha)\%$ CI and p-value will be presented.

- A multivariate stratified (by factors as specified in [Section 2.2](#)) Cox model will be fitted to assess the treatment effect when adjusted for potential prognostic factors. The following potential prognostic factors will be included in the model. A backward selection approach, starting from the full model, will be used as primary method with a significance level set to 0.10 of each of the covariates.
 - Age categorization ($< 65, \geq 65$)
 - Gender (Male vs. Female)
 - Baseline ECOG PS (0 vs. 1)
 - Region (Asia vs. RoW [including US/Canada, Europe])
 - Disease at study entry (EC vs. GEJ)
 - Time from beginning of neoadjuvant CRT to complete resection (< 6 weeks vs. ≥ 6 weeks)
 - Time from complete resection to randomization (< 10 weeks vs. ≥ 10 weeks)

If there is more than 10% imbalance between two arms within the subgroup of baseline demographics and disease characteristics, the factor may also be considered in the adjusted multivariate model.

For the multivariate analysis, HR and 95% CI will be provided for treatment variable and all covariates. Descriptive p-values will be provided.

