7.5.3 Secondary Efficacy Endpoints

7.5.3.1 Primary Analysis of OS

One of the secondary objectives of the study is to compare the overall survival between treatment groups in all randomized subjects.

Overall survival will be compared between the treatment groups at the two interim looks and final analyses, using the log-rank test, stratified by the three randomization stratification factors as recorded in IWRS. An O'Brien and Fleming α -spending function will be employed to determine the nominal significance levels for the interim and final analyses. The stratified hazard ratio between the treatment groups will be presented along with $100*(1-\alpha)\%$ CI (adjusted for interim). In addition, two-sided p-value will also be reported for the analysis of OS.

OS will be estimated using the KM techniques. A two-sided 95% CI for median OS in each treatment group will be computed via the log-log transformation method. OS rates at fixed time points (e.g. 6 months, depending on the minimum follow-up) will be presented along with their associated 95% CIs. These estimates will be derived from the Kaplan-Meier estimate and corresponding CIs will be derived based on Greenwood formula¹⁵ for variance derivation and on log-log transformation applied on the survivor function¹⁶.

The status of subjects who are censored in the OS KM analysis will be tabulated for each treatment group using the following categories:

- On-study (on-treatment, in follow-up)
- Off-study (lost to follow-up, withdraw consent, never treated)

A by-subject listing will be presented including treatment group, first and last dose date, whether the subject died, and if censored, the reason, event/censored date and OS duration.

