7.5.3.2 Sensitivity Analyses

- The sensitivity analysis specified in [section 7.5.2.1](#) will also be performed for OS when applicable. The sensitivity analyses specific for DFS will not be performed for OS.

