9 DOCUMENT HISTORY

Table 9-1: Document History

Version Number	Author(s)	Description
1.0 Apr 25, 2017		Original Issue based on revised protocol 01 dated Aug 24, 2016

Table 9-1: Document History

[figure not shown]
[figure not shown]

2.0 Oct 24, 2019
		
Based on revised protocol 03 dated June 06, 2019. The following changes are made in the SAP amendment to reflect the protocol amendment of having DFS as the primary endpoint, and OS as the secondary endpoint.  .
 
 • Objectives and endpoints to keep DFS as the sole primary endpoint and change OS to the secondary endpoint • Sample size and power • Schedule of analyses • The method to maintain blinding of OS if not positive at two interim looks of the studyThe method for alpha spending between IA and FA for DFS and OS PFS2 definition and analyses 
The SAP amendment also incorporates the IO core SAP.

3.0 May 4, 2020
		
Minor updates from SAP version 2.0 to add sensitivity analyses in Section 7.5.2.1 and other minor edits. Details are summarized below.
 
 • • Remove dose reduction in Section 7.6.4 as it is not applicable in this study. • Include in 7.5.2.2 Consistency of Treatment Effect in Subsets, Pathologic tumor status (ypT0, ypT1/ypT2, ypT3/ypT4, unknown) • Remove cumulative plot of baseline PD-L1 expression in section 7.8 as it is not very informative. • Remove the log-rank test and keep the Cox model for the subgroup analysis by PD-L1 status in section 7.8. • Add "c) no on-study disease assessment but death with prior subsequent therapy or second primary cancer" for censored on randomization date in section 7.5.2

4.0 Sept 30, 2020
		
Minor format update on hyperlinks, references, and page numbers. Correction of the relative dose intensity formula in Table 7.4-1 Administration of study therapy: definition of parameters.

Table 9-1: Document History

--	--	--

APPENDIX 1 TIME-TO ONSET AND TIME-TO RESOLUTION DEFINITION AND CONVENTIONS FOR SELECT ADVERSE EVENTS, IMMUNE-MEDIATED ADVERSE EVENTS AND EVENTS OF SPECIAL INTEREST

Time-to onset definition

Time-to onset of AE (any grade) for a specific category is defined as the time between the day of the first dose of study treatment and the onset date of the earliest AE (of any grade) in this category.

The time-to onset of AE (grade 3-5) for a specific category is defined similarly with an onset date corresponding to a grade 3-5 AE.

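### Protocol 8.4.2.4 gives the DMFS and PFS2 hazard ratios without the three randomization strata that the SAP uses for DFS and OS; with a real effect and prognostic strata they fall, on average, slightly nearer 1

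*Protocol*

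**What the plan says.** - **DMFS and PFS2 (Protocol 8.4.2.4):** "The HR for DMFS and PFS2 will be estimated via a Cox model with treatment arm as the only covariate in the model". The sentence is complete and unredacted.
- **DFS (SAP 7.5.2):** the HR "will be estimated via a stratified Cox model with treatment arm as the only covariate in the model". The log-rank test beside it is stratified by the three randomization factors as held in IWRS: PD-L1 status, nodal status and histology.
- **OS (SAP 7.5.3.1):** "The stratified hazard ratio between the treatment groups will be presented along with" an interim-adjusted confidence interval.
- **Where the SAP intends no strata, it says so.** SAP 7.5.2.1 lists, as a DFS sensitivity analysis, "Analysis using a 2-sided, un-stratified log-rank test and an un-stratified Cox proportional hazards model with treatment as the single covariate". SAP 7.5.3.2 extends the general sensitivity analyses to OS; they "will also be performed for OS when applicable".

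Protocol 8.4.2.2 and 8.4.2.3, which would give the protocol's own DFS and OS models, are blacked out. The SAP contents list passes from 7.5.3.5 to 7.5.5, so no DMFS or PFS2 model can be read there. The SAP document history does record "PFS2 definition and analyses" among the version 2.0 changes.

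**The concern.** Taken at face value, 8.4.2.4 gives two exploratory endpoints, as their only stated HR, the kind of model that the SAP uses for DFS and OS only as a sensitivity analysis. An unstratified Cox model estimates a marginal HR and a stratified one estimates a within-stratum HR. Because the HR is non-collapsible, the two differ whenever the effect is non-null and the strata predict outcome, even with perfect balance. Protocol 1.4.7.7 says that positive nodes carry worse survival, so prognostic strata are to be expected.

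What is at stake is comparability. DMFS counts distant recurrence or death (Protocol 8.3.3), overlaps heavily with DFS, and will naturally be read beside it. On PFS2, the rationale for Revised Protocol 03 remarks that "PFS2 has recently been proposed as a surrogate for OS, particularly for trials evaluating maintenance therapy", which invites comparison with OS. Part of any small gap between such HRs would then come from the model and not from the endpoint.

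**Working it through.** **Scale check against the plan.** Protocol 8.4.2.4 states no figure, so the nearest stated one is the power in SAP 5.3.

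- DFS: 440 events, 2:1 allocation, HR 0.72, two-sided 0.05. √(440 × 1/3 × 2/3) × |ln 0.72| − 1.960 = 9.888 × 0.3285 − 1.960 = 1.288, giving 90.1% (stated: approximately 91%).
- OS: 460 events, HR 0.73. √(460 × 2/9) × |ln 0.73| − 1.960 = 1.222, giving 88.9% (stated: approximately 90%).
- Group-sequential versions give 89.6% and 88.2%. All are within two points of the plan.

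**How prognostic is nodal status?** Protocol 1.1 gives 5-year survival of 37% for non-pCR subjects and 17% for node-positive subjects. With node-positive share p, node-negative survival is (0.37 − 0.17p)/(1 − p), and the implied nodal HR is ln(0.17)/ln[(0.37 − 0.17p)/(1 − p)].

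- p = 31%: ln 0.17 / ln 0.460 = 2.28
- p = 45%: ln 0.17 / ln 0.534 = 2.82
- p = 58%: ln 0.17 / ln 0.646 = 4.06

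The share in this trial is an assumption. The 31% comes from a trial arm described in Protocol 1.4.3 that included pCR subjects. Nodal HRs of 1.5 and 2.0 were added as weaker cases.

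**Simulation A: nodal status only.** There were 2,000 trials per setting: 760 subjects, 2:1 in blocks of 6 within nodal stratum, 36-month uniform accrual, data cut at 58 months. Overall control hazards follow SAP Table 5.1-1 (0.035, 0.03, 0.02, 0.003 per month) as a stand-in, because no DMFS or PFS2 rates are given. Constant within-stratum HR 0.72, 455–466 events:

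| Share / nodal HR | Unstratified HR | Stratified HR | Paired ratio | Mean log-HR difference (SD) | Unstratified nearer 1 |
|---|---|---|---|---|---|
| 45% / 1.5 | 0.727 | 0.724 | 1.005 | 0.005 (0.011) | 68% |
| 45% / 2.0 | 0.731 | 0.719 | 1.017 | 0.016 (0.018) | 83% |
| 31% / 2.28 | 0.736 | 0.720 | 1.022 | 0.022 (0.022) | 85% |
| 45% / 2.82 | 0.745 | 0.718 | 1.037 | 0.037 (0.028) | 92% |
| 58% / 4.06 | 0.760 | 0.718 | 1.058 | 0.057 (0.033) | 97% |

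HRs are geometric means; ratios use unrounded values. The standard error of the log HR is 0.096–0.097 under either model.

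SAP 5.2 expects a late effect: "the treatment effect for DFS is assumed to have a delayed separation with an HR of 1 for the first 3 months", then 0.667. Under that pattern the ratios are 1.005, 1.016, 1.020, 1.033 and 1.056, with the unstratified HR nearer 1 in 67% to 96% of trials. With no treatment effect the ratio is 0.999–1.001.

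**Simulation B: all three factors, eight strata.** Assumed shares are 55% node-positive, 70% adenocarcinoma and 30% PD-L1 ≥ 1%. Assumed prognostic HRs (node, adenocarcinoma, PD-L1) are weak 1.3/1.1/1.1, moderate 1.7/1.3/1.2 and strong 2.6/1.9/1.5. Each large-sample run has 1,000,000 subjects; entries are stratified → unstratified HR:

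| Strata | Constant HR 0.72 | SAP DFS hazards | SAP OS hazards |
|---|---|---|---|
| Weak | 0.721 → 0.724 | 0.715 → 0.717 | 0.728 → 0.730 |
| Moderate | 0.718 → 0.727 | 0.715 → 0.724 | 0.727 → 0.734 |
| Strong | 0.723 → 0.752 | 0.717 → 0.741 | 0.730 → 0.754 |

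The shift is about 1%, 3–4% and 10–12% of the log HR. With non-prognostic strata the two models agree exactly, and under a null effect both give about 1.00. At 760 subjects and HR 0.72 (1,500 replicates) the mean log-HR shifts are 0.003, 0.012 and 0.040 against standard errors of 0.095–0.099. The unstratified HR is nearer 1 in 57%, 73% and 91% of replicates.

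**The case against.** The strongest reply is that the protocol is silent on strata, not opposed to them. SAP 7.5.2 calls treatment the only covariate in a model that is stratified, so that phrase excludes nothing. The SAP carries the operative detail, its PFS2 analyses exist but cannot be read, and redacted text is not missing from the plan. This stands, and it is why the point is confined to the protocol sentence.

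It is also true that the unstratified HR is a legitimate estimate, that any average shift is conservative, that the endpoints carry no alpha, and that no document plans a formal comparison of the PFS2 and OS HRs. Protocol Appendix 5 gives EMA guidance as the reason for adding PFS2; the surrogacy remark is supporting background. The unstratified DFS and OS sensitivity analyses would supply like-for-like figures, though not against the primary HRs. All of this limits the importance of the point without removing it.

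Last, a protocol change needs ethics committee approval (Protocol 9.1.1), and the first interim analysis is already complete according to the rationale for Revised Protocol 04. That calls for dating the change. It is a minor obstacle, because the strata were fixed at randomization and no formal test depends on them.

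**Conclusion.** The point holds, as a minor improvement. As written, Protocol 8.4.2.4 gives unstratified DMFS and PFS2 HRs beside stratified DFS and OS HRs. The average effect is a ratio of unstratified to stratified HR between 1.005 and 1.058 over the nodal strengths examined, the top value being an upper extreme. The mean shift is below one standard error throughout. It requires a non-null effect and prognostic strata, and it describes the average, not every dataset. Type I error, power and sample size are untouched.

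The size rests on assumed node-positive shares, assumed prognostic strengths, and DFS or OS hazards standing in for DMFS and PFS2. The direction held in every non-null setting with prognostic strata. Whether the SAP as a whole stratifies these endpoints cannot be judged from the public copy.

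**What to change.** In Protocol 8.4.2.4, specify a Cox model stratified by the three randomization factors as recorded in IWRS, with treatment arm as its single covariate. Confirm that the SAP section on DMFS and PFS2 says the same, and align it if not. Date the change; if either HR has already been produced without strata, report both versions.

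The cost is one phrase, carried through the usual amendment approval. The factors are already in IWRS, no new data are needed, and the simulated standard errors show essentially no loss of precision.
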